Centers:	Sørlandet Hospital + 5-10 other Norwegian hospitals
Study Period:	Estimated date of first patient enrolled: 01.10.15 Anticipated recruitment period: 01.10.15- 31.12.19 Estimated date of last patient completed: 31.12.20
Treatment Duration:	Six weeks
Follow-up:	13 months
Objectives	
Primary objective
 
To answer the question “is two weeks doxycycline treatment (currently suggested treatment) at least as effective as six weeks doxycycline treatment in Lyme Neuroborreliosis?”
 
Key secondary objectives
 
To provide a better understanding of the pathogenesis and long-term complaints, and to search for new biomarkers in LNB
 
To collect clinical data, blood, and CSF in a biobank for future research

Endpoints:	
Primary endpoint:
 
Improvement in composite clinical score defined as clinical score at inclusion minus clinical score at 6 months.
 
Secondary endpoints:
 
Fatigue Severity Scale (FSS) Patient Health Questionnaire (PHQ-15) Short Form 36 (SF-36) Blood and CSF findings MRI, and neuropsychological assessments in a subset of patients Adverse events

Study Design:	Multicenter, non-inferiority, randomized, penta-blind, placebo-controlled trial
Main Inclusion Criteria:	
1. Neurological symptoms suggestive of LNB without other obvious reasons and one or both of
a. Cerebrospinal fluid pleocytosis (≥ 5 leukocytes/mm³)b. Intrathecal Bb antibody production2. Signed informed consent
Main Exclusion Criteria	
- Age less than 18 years- Pregnancy, breast-feeding- Adverse reaction to tetracyclines- Treatment with cephalosporin, penicillin, or tetracycline the last 14 days- Serious liver or kidney disease that contraindicates use of doxycycline- Lactose intolerance- Need to use medications contraindicated according to SmPC of the IMP
Sample Size:	120 patients
Efficacy Assessments:	Comparison of clinical outcome six months after end of treatment between the two treatment groups.
Safety Assessments:	Subjective experiences and blood tests including hematology and biochemistry for four weeks after ended treatment.

TABLE OF CONTENTS

CONTACT DETAILS.....	2
SIGNATURE PAGE	3
PROTOCOL SYNOPSIS.....	4
TABLE OF CONTENTS	5
LIST OF ABBREVIATIONS AND DEFINITIONS OF TERMS.....	8
1 INTRODUCTION.....	9
1.1 Background – Lyme Neuroborreliosis (LNB).....	9
1.2 Background - Therapeutic Information.....	9

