1.4 Rationale for the Study and Purpose

The main purpose of the trial is to answer the “is two weeks doxycycline treatment (currently suggested treatment) at least as effective as six weeks doxycycline treatment in LNB?” The benefits of a positive answer to this question would

be a reduced frequency of persisting complaints after treatment. The benefits of a negative answer would be avoidance of unnecessarily prolonged treatment with antibiotics and thereby reduced antibiotic resistance. Doxycycline 200 mg daily for 2 weeks is recommended for LNB, and half of the study patients will receive this standard treatment (and additional four weeks of placebo). The other half will receive doxycycline 200 mg daily for six weeks. Possible disadvantages for the trial participants are more adverse advents as nausea and diarrhea, disturbances in leukocyte and thrombocyte count, and skin reactions (mostly photosensitivity). Longer antibiotic treatment may also lead to higher prevalence of resistant bacteria in patients and the general society. We regard these possible disadvantages as minor as the patients' subjective experiences and blood cell count will be closely monitored during the study, and both groups of patients will be discouraged sunbathing during treatment and up to two weeks after drug intake. In our opinion, the benefit of determination of preferred duration of treatment for the future eliminates the disadvantage of exposing. Besides this, several spin off effects strengthens the rationale for conducting the study. The collected clinical data and specimens (blood and CSF) from well-characterized LNB patients may enable us to address other hypotheses regarding long-term complaints as immune dysregulation, genetic predisposition, co-infections and structural changes in CNS, and it facilitates search for new biomarkers of LNB which could be used in diagnostics.

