2.2 Secondary Endpoints

Improvement of composite clinical score from inclusion to 12 months after end of treatment defined as clinical score at inclusion minus clinical score at 12 months. (Table1)

Fatigue Severity Scale (FSS) at six and 12 months after end of treatment. FSS is translated and validated for Norwegian purposes (12). It measures level of agreement (1– 7) with nine statements. The final score represents the mean value of the nine items. Severe fatigue is defined as a score >5 in a Norwegian population. Reported mean score in 20 American

healthy adults is 2.3 (13), and reported mean score in 50 Norwegian patients treated for LNB is 3.5 versus 2.1 in the control group (3).

Patient Health Questionnaire (PHQ-15) at six months. PHQ-15 is a brief, validated questionnaire, which consists of 13 questions concerning severity of different subjective somatic symptoms the last 4 weeks, and 2 questions concerning sleep and tiredness. Each item is scored from 0 to 2, and sum score ranges from 0 to 30. Sum scores of 5, 10, and 15 represent cutpoints for low, medium, and high symptom severity, respectively (27).

Short Form-36 (SF-36): SF-36 is a valid and reliable questionnaire assessing health related quality of life. It consists of 36 questions concerning general health perceptions, physical functioning, physical role functioning, emotional role functioning, social role functioning, bodily pain, vitality and mental health. A Norwegian normal material exist (28).

CSF findings at six and 12 months: Cell count, IgG index, OCB's, and *Bb* antibodies

Other laboratory tests, MRI, and neuropsychological assessments: In a subset of patients at inclusion and six months after end of treatment (WP4 of BorrSci).

Safety as measured by serious adverse events and less serious side effects of treatment (Table 3)

Table 3. Safety measures

Treatmentweek	0	1	2	3	4	5	6	7-10
Nausea		x	x	x	x	x	x	x
Vomiting		x	x	x	x	x	x	x
Diarrhea		x	x	x	x	x	x	x
Skin reactions		x	x	x	x	x	x	x
Vaginitis		x	x	x	x	x	x	x
Blodtests (Hb, Hb, white blood cell count with differential, platelet count, ASAT, ALAT, GT, ALP, Creatinine)	x		x		x			
Other AE or complications		x	x	x	x	x	x	x

Secondary and exploratory objectives and their endpoints and assessments are detailed in WP 3 and 4 (Appendix A)

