6 STUDY PROCEDURES

6.1 Flow Chart

Time	Baseline	Treatment and post-treatment Period Week 1-10					Follow-up Period	
		Once weekly	Week 2 - 4	Day 6-8 after start of treatment	End of week 10	6 months after end of treatment	12 months after end of treatment	
Enrollment and Informed consent	x							
Basic demographics	x							
Medical History	x							
Concomitant medications	x					x	x	

Time	Baseline	Treatment and post-treatment Period Week 1-10					Follow-up Period	
		Once weekly	Week 2 - 4	Day 6-8 after start of treatment	End of week 10	6 months after end of treatment	12 months after end of treatment	
Telephone to check for reasons to discontinue IMP (treatment failure, toxicity, and so on)				x				
Composite clinical score (Table 2)	x				x	x	x	
FSS	x				x	x	x	
PHQ-15						x	x	
SF-36						x		
CSF sampling	X**					x	x	
Blood sampling	X**					x	x	
IMP delivery	x							
Patientregistration of compliance, concomitant medication, and adverse events (Table 3)		x						
Bloodtests to check toxicity of treatment	x		xx					
Pill count and collection of patients diaries					x			
Cerebral MRI*			x				x	
Neuropsychological screening tests*			x					
Neuropsychological testing*						x		

Table 5. Trial flow chart

*a subset of patients (WP4)

** obtained by clinican before inclusion

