6.2.2 During Treatment

- Adverse events: Diary (on paper or electronic - optional) every week until four weeks after ended treatment
- Registration of concomitant medications
- Blood analyses 2 and 4 weeks after treatment start (Hb, white blood cell count with differential, platelet count, ASAT, ALAT, GT, ALP, Creatinine)
- Talk (meeting or telephone, optional) 1 week after treatment start to uncover reasons for discontinuation of IMP (deterioration, progression or other - see 6.3)
- Non-scheduled visit in case of disease progression SAE or SUSAR
- Cerebral MRI and neuropsychological screening in a subset of patients (see APPENDIX A)

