6.2.3 End of Treatment Visit (four weeks after ended treatment)

- Counting and relinquishment of remaining pills
- Collection of patients diary
- Registration of symptoms, concomitant medication, and adverse events
- Composite clinical score
- FSS

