6.2.5 Six months After End of Treatment (Follow-up)

- Interview about symptom description, concomitant medication, and sick leave attributable to LNB
- Composite clinical score
- FSS, PHQ-15, SF-36
- Laboratory analyses
 - Blood: Hb, white blood cell count with differential, platelet count, ASAT, ALAT, GT, ALP, Creatinine, CRP, electrophoresis, Bb antibodies, TBE antibodies
 - CSF: Cellcount, protein level, Oligoclonal bands, Bb antibodies,
 - In addition aliquots of specimens will be transferred for biobank storage
- Cerebral MRI and neuropsychological testing in a subset of patients (Appendix A)

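### Safety blood tests are scheduled to stop at week 4 of a six-week course, although the synopsis has them run until four weeks after treatment

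*Combined protocol and SAP*

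**What the plan says.** The Safety Assessments row of the protocol synopsis reads "Subjective experiences and blood tests including hematology and biochemistry for four weeks after ended treatment". The rest of the protocol sets out the sampling as follows.

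- **Section 2.2, Table 3.** The row "Blodtests (Hb, Hb, white blood cell count with differential, platelet count, ASAT, ALAT, GT, ALP, Creatinine") is marked at treatment weeks 0, 2 and 4. It is blank at weeks 5, 6 and 7-10. The symptom rows of the same table are marked every week from week 1 through weeks 7-10.
- **Section 6.1, flow chart.** The row "Bloodtests to check toxicity of treatment" has one mark at baseline and two under the week 2-4 column. It has none at the end of week 10.
- **Section 6.2.2.** The text lists "Blood analyses 2 and 4 weeks after treatment start".
- **Section 6.2.3, the visit four weeks after treatment.** It has a pill count, diary collection, "Registration of symptoms, concomitant medication, and adverse events", the composite score and the FSS. There is no laboratory item.
- **Section 6.2.5, six months after treatment.** The panel returns within the follow-up laboratory work: "Blood: Hb, white blood cell count with differential, platelet count, ASAT, ALAT, GT, ALP, Creatinine, CRP, electrophoresis", with serology. Section 6.2.6 repeats it at 12 months.

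Section 1.4 names "disturbances in leukocyte and thrombocyte count, and skin reactions" among the possible disadvantages of taking part. It regards the disadvantages as minor, partly because "blood cell count will be closely monitored during the study".

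**The concern.** The two arms receive the same drug for two weeks and differ only in weeks 3 to 6, when one takes doxycycline and the other placebo. Safety is listed among the secondary endpoints under the primary objective, so laboratory tolerability of the extra four weeks is part of what the trial should inform. The synopsis tells an ethics committee or regulator that haematology and biochemistry are followed until week 10. A site working from the schedule will take its last safety sample at week 4, while the longer course is still running. For a patient with no earlier doxycycline, there is then no scheduled blood test at or after the end of that course until the six-month visit. The issue is whether the plan carries out the safety monitoring it describes. The primary endpoint does not depend on it.

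**Working it through.** The plan gives no figure to reproduce. The check sets the sources side by side and counts weeks. Unless stated otherwise, weeks run from the first dose in a patient with no doxycycline before inclusion.

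| Source | Safety blood tests |
|---|---|
| Synopsis | until four weeks after treatment |
| Table 3 | weeks 0, 2, 4 |
| Flow chart | baseline, two within weeks 2-4 |
| Section 6.2.2 | weeks 2 and 4 |
| Section 6.2.3 (week 10) | none |
| Sections 6.2.5 and 6.2.6 | six and 12 months after treatment |

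1. **End of the stated window.** Six weeks of treatment (section 5.3) plus four weeks gives 6 + 4 = week 10.
2. **Part of the window after the last sample.** 10 − 4 = 6 of 10 weeks: the last two treatment weeks and all four weeks after treatment.
3. **Time to the next panel.** Taking six months as 26 weeks, the visit falls at 6 + 26 = week 32, which is 32 − 4 = 28 weeks after the last safety sample.
4. **Could text extraction explain this?** No. Section 6.2.2 is prose and agrees with both tables.
5. **Does earlier doxycycline change it?** Section 5.6 allows inclusion after doxycycline has started, and section 6.2.2 does not say whether treatment start means the first doxycycline dose or the first study capsule. Assume at most 14 earlier days; section 5.6 sets no limit. Counted from the first capsule, the last sample then falls on doxycycline day 28 + 14 = 42, the last treatment day. Counted from the first dose, it stays at day 28. Either way, no sample falls in the 28 days after treatment (days 43-70).
6. **What a week-10 sample would find.** It detects anything present on day 70. An abnormality starting on day 42 must last 70 − 42 + 1 = 29 days to be seen; one starting on day 29 must last 70 − 29 + 1 = 42 days. Shorter ones would be missed.

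**The case against.** The strongest reply is that this is a loose synopsis line and not a deficient schedule. Three operative sources agree, the safety endpoint is defined by reference to Table 3, and correcting one sentence would remove the inconsistency. The time phrase might also be meant for the subjective reports alone, since the diary does run to four weeks after treatment. Existing cover is substantial: the week-4 sample falls two weeks into the period when the arms differ, adverse events are followed to resolution, the diary is weekly, and the panel at six and 12 months would show a persistent abnormality. Section 1.3 describes a well-known drug with a good safety profile.

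Much of this stands, and it is why the gap is narrow. It does not remove the gap. As written, the time phrase covers the blood tests too. Rewording the synopsis would make the document consistent by withdrawing the stated check, leaving the end of the longer course and the period after it without a scheduled blood test. The diary cannot reveal an abnormality without symptoms, and the six-month panel cannot reveal one that has already resolved.

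A reader might also infer that the adverse-event rules require these samples. They do not. Section 8.1.1 (Adverse Event) counts abnormal laboratory findings, section 8.2 lists blood-test disturbances as expected, and section 8.4 sets the recording period. None of them orders a scheduled draw, and an abnormal result from a clinically indicated test would still be recorded. Section 1.4 likewise promises no post-treatment sample. It speaks of blood counts only, not liver tests or creatinine, and it also relies on symptom reports and sun avoidance. It gives a reason to keep the monitoring but does not prove a breach.

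**Conclusion.** The point holds as a mismatch between the stated safety assessment and the schedule, with a narrow practical gap. No scheduled test detects abnormalities in blood count, liver tests or creatinine that cause no symptoms, begin after week 4 and resolve before six months. That no sample is scheduled in the four weeks after treatment holds under both readings of treatment start, with up to the assumed 14 days of earlier doxycycline.

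Two stronger conclusions are tempting but unsupported. The first is that laboratory harm will be missed. The counts above are calendar intervals, and the documents give neither a rate nor a timing for late laboratory toxicity. The second is that half of the extra exposure goes untested. The 14 of 28 differing days (50%) after the last sample apply to a patient with no earlier doxycycline, or when weeks are counted from the first dose. Counted from the first capsule after 14 earlier days, the share is 0 of 28. The range is 0-50% and rests on that assumed maximum and on an undefined starting point.

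The primary endpoint and its analysis are unaffected. The point merits a correction because the remedy is cheap and delivers what the synopsis already states.

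**What to change.** Add the existing safety panel (Hb, white cells with differential, platelets, ASAT, ALAT, GT, ALP and creatinine) to the week-10 visit, and enter it in Table 3, the flow chart and section 6.2.3 so that the schedule matches the synopsis.

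The cost is one routine local-laboratory sample per patient: 120 × 1 = about 120 panels, with no extra visit. Its limitation is that an abnormality that began in weeks 5-6 and resolved before week 10 can still be missed. A draw at week 6 would catch anything present when the longer course ends, but no visit is scheduled then and each patient would need an extra attendance. It is optional and not part of the required change.

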11.4	Audit and Inspections.....	22
12	ETHICAL AND REGULATORY REQUIREMENTS.....	22
12.1	Ethics Committee Approval.....	22
12.2	Other Regulatory Approvals	22
12.3	Informed Consent Procedure.....	22
12.4	Subject Identification	23
13	TRIAL SPONSORSHIP AND FINANCING	23
14	TRIAL INSURANCE	23
15	PUBLICATION POLICY	23
16	REFERENCES	24
17	LIST OF APPENDICES.....	25

LIST OF ABBREVIATIONS AND DEFINITIONS OF TERMS

Abbreviation or special term	Explanation
AE	Adverse Event
AR	Adverse Reactions
Bb	Borrelia burgdorferi
CIOMS	Council for International Organizations of Medical Sciences
CNS	Central Nervous System
CONSORT	Consolidated Standards of Reporting Trials
CRF	Case Report Form (electronic/paper)
CSF	Cerebrospinal Fluid
CSR	Clinical Study Report
CTC	Common Toxicity Criteria
CTCAE	Common Terminology Criteria for Adverse Event
CTU	Clinical Trial Unit
DAE	Discontinuation due to Adverse Event
DMC	Disease Monitoring Committee
EC	Ethics Committee
FSS	Fatigue Severity Scale
GCP	Good Clinical Practice
ICF	Informed Consent Form
ICH	International Conference on Harmonization
IMP	Investigational Medicinal Product (includes active comparator and placebo)
ISF	Investigator's Study File
ITT	Intention to treat
LNB	Lyme Neuroborreliosis
MRI	Magnetic Resonance Imaging
NMA	Norwegian Medical Agency
NTNU	Norwegian University of Science and Technology
OUS	Oslo Universitetssykehus
PHQ-15	Patient Health Questionnaire
PNS	Peripheral Nervous System
SAE	Serious Adverse Event
SDV	Source document verification
SF-36	Short Form 36
SmPC	Summary of Product Characteristics
SOP	Standard Operating Procedure
SSHF	Sørlandet Sykehus HF
SUSAR	Suspected Unexpected Serious Adverse Reactions
TMF	Trial Master File
WP	Work Package

1 INTRODUCTION

1.1 Background – Lyme Neuroborreliosis (LNB)

Lyme borreliosis is a multisystem infectious disease, caused by the tick-borne spirochete *Borrelia burgdorferi* (*Bb*), which frequently affects the nervous system. The most common clinical manifestations of European Lyme Neuroborreliosis (LNB) are painful radiculitis and cranial neuropathy (most often the facial nerve). Rarer manifestations are myelitis, encephalitis, and peripheral neuropathies. The diagnosis of LNB is based on a combination of clinical neurological findings, lymphocytic pleocytosis and intrathecal *Bb* antibody production (1).

Most patients recover well within weeks to a few months after standard antibiotic treatment, but 25-50% of LNB patients report residual complaints often labelled post-Lyme syndrome (2-9). The most common remaining complaints are subjective symptoms as fatigue, pain, concentration and memory problems. Remaining objective findings as facial palsy and radiculopathy are rarer.

The impact and prevalence of post-Lyme syndrome are debated, as similar symptoms are common in the general population. It is also questioned if the complaints are more common after LNB than after other infections in the nervous system. There are few controlled studies on the issue, but one previous study found more fatigue and lower mean scores on health related quality of life among 50 well-characterized LNB patients 30 months after treatment for LNB than among 50 matched healthy controls (3).

The underlying mechanism of post-Lyme syndrome is also debated and largely unresolved. Theories as ongoing chronic *Bb* infection (10), dysregulated immune responses (11, 12), genetic predisposition (13), co-infection with multiple tick-borne pathogens (14), structural changes in the Central Nervous System (CNS) (15), and personal traits (16, 17), have been suggested.

In the current trial, we will address the persistent infection hypothesis by assessing long-term prognosis after extended antibiotic treatment. Further, the trial is a part of the compound and large BorrSci study (Lyme borreliosis; a scientific approach to reduce diagnostic and therapeutic uncertainties) which also aims to address the other hypotheses mentioned above. These approaches are further described in the protocols for the other workpackages (WP) of BorrSci (Appendix A). The blood and cerebrospinal fluid (CSF) specimens along with comprehensive clinical information collected from the patients included in the current treatment trial is an important contribution to the biobank that will be established for these purposes.

1.2 Background - Therapeutic Information

Standard treatment for Lyme Neuroborreliosis (LNB) is intravenous ceftriaxone or penicillin, or oral doxycycline for two to four weeks (1). Previous studies have shown that two weeks of oral doxycycline and intravenous ceftriaxone are equally effective for LNB with painful radiculitis or cranial neuritis (5, 18). However, evidence about the optimal duration of treatment is currently lacking. There are a few studies of prolonged antibiotic treatment in LNB, but they are hampered with poorly-characterized patients, insufficient statistical power, lack of matched controls, and ambiguous results (19-23). A case series reported excellent or good response in 90% of patients with disseminated Lyme (including some with neuroborreliosis) after treatment with oral cefixime or IV ceftriaxone for 14 days followed by oral amoxicillin for 100 days (24). A controlled study of 152 patients with disseminated Lyme disease (including 62 with neuroborreliosis) (20), however, found similar outcome in patients treated with 3 weeks with IV ceftriaxone followed by oral amoxicillin for 100 days and patients treated with 3 weeks IV ceftriaxone followed by placebo for 100 days. An American openlabel randomized comparison of 14-days versus 28-days treatment with ceftriaxone for late Lyme borreliosis (143 patients, of whom a third with neurological symptoms), showed more treatment failures in the 14-day group than in the 28-day group, but did not have the power to determine if a clinical subset of patients may benefit from 28 days of therapy. There were more discontinuations because of adverse events in the 28- days group (25). Another series of late LNB showed disappearance of symptoms in 87% after 100 days regimens with various antibiotics, whereas 14 days with ceftriaxone cured 31% (26).

The possibility that a longer treatment with doxycycline, such as six weeks, is superior to the current standard treatment of two weeks in LNB has not been properly addressed in a randomized controlled trial.

